A number of subjects who fulfil the criteria will be invited to participate in this study. The study will involve arch width analysis using study models pre, post-debond, 3 months review post-debond, 6 months review post-debond and 12 months review post-debond. All data will be analyses using Statistical Package for Social Sciences (SPSS). The arch width of subjects post-fixed appliances will be compared. Most studies compare the arch width, as well as lower incisor irregularity in evaluating relapse in different groups of retainers. However, there are currently no randomized control trials comparing expansion cases of Hawley vs vacuum formed retainers, hence why this study will be conducted.

We expect to see no difference between the modified vacuum formed retainer and Hawley retainer in terms of maintaining arch expansion post-orthodontic treatment. This would therefore mean that there would be a simpler method and would be a suitable more cost-effective alternative as compared to constructing Hawley retainers or adding a palatal wire on the vacuum formed retainers.

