5.0 METHODOLOGY

5.1 Participants Sampling

The sample will be selected from patients attending for orthodontic debond appointments at the Orthodontic Unit of Universiti Kebangsaan Malaysia (UKM), Klinik Pakar Ortodontik Klinik Kesihatan Bandar Botanik and Unit Pakar Ortodontik Klinik Pergigian Sungai Chua patients. The present practice at all 3 locations constructs Hawley and normal VFR retainers for all orthodontic patients. There are technicians and laboratory facilities to construct normal VFR as well as Hawley retainer. The only difference between modified and normal vacuum formed retainer is the outline of the retainers where the technician would trim the retainer, where it would cover the hard palate. Therefore it is only the location of trimming that is different using the same special trimming appliances for normal VFRs. Clinicians from KKM involved would be [name] [name] and [name] [name]. A screening will be done to select patients who are suitable of the study. Only patients who fulfil the criteria will be invited to participate in this study. Participant will be approached in the dental chair once deemed suitable, and will be given 5-10 minutes to decide on participation of the study. Consent will be gathered from the patients or the carer if the patient is below 18 years of age. The patients will then be randomly allocated into two groups using a randomized number computer generator, either the Hawley or the modified vacuumed formed retainers. The expected sample size to be of statistical significance will be calculated using the formula of sample size calculation relevant to this study. The sample size

calculation is based on a significance level of 0.05 and 80 percent power to detect a clinically meaningful difference of 2.0mm (SD=2.0mm) between the two groups in terms of arch width differences, where this difference are based on previous studies by Tynelius et al. (9) and Shawesh et al. (15). The power analysis gave a total sample size of 16 patients in each group. To account for attrition, 24 patients will be recruited in each group

The inclusion criteria of the subjects that will be included in the study are:

- a. Patients who are at least 13 years old at time of debond.
- b. Treatment plan of extraction or non-extraction followed by straight wire appliances in the upper arch only or both arches

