5.2 Study design

This is a prospective randomised controlled trial to evaluate the differences in relapse after expansion treatment between a Hawley and a modified vacuum formed retainer.

The study will involve:

- a. **Clinical:** An upper and lower impression with alginate will be taken for dental cast and retainer construction. **This procedure is a normal procedure done in all orthodontic appointments upon removal of fixed appliances.** However one extra upper impression will be taken for the research. It will take approximately 5-10 minutes. **All retention appliances will be distributed within 24 hours after debonding. The retainers will be washed under tap water before delivering to the patient. When subjects are given the retainers, clinicians will provide post-debond instructions, where the patient has to wear the retainers for 24 hours except during eating and brushing their teeth. Researcher will send reminders of wearing retainer in 1-month interval to ensure they are following the instructions and to enquire if they have any problems.** The patients will be instructed to wear the retainers for 24 hours for the next 6 months and night-time only for month 7 to month 12. At a 3 month and 6 month follow-up, an upper alginate impression will be taken for a dental cast construction at each follow-up visit. **Clinical examination will allow clinician to detect relapse which is by examining the arch width.** The whole duration of participation of each patient may total up to 40 minutes overall. If any unknown allergic reaction to alginate impression occurs, the procedure will be terminated immediately and appropriate first aid action will be given to participant, however these will most likely be anticipated as these subjects have had impressions taken at the start of treatment.
- b. **Data Measurement:** Dental casts will be analysed using digital callipers and arch width will be recorded in the posterior region.
- c. **Data analysis:** Data will be analysed using SPSS. The descriptive statistics on group level at times corresponding to measurements at removal of fixed appliances (T0), 3 months post retention (T1), 6 months post retention(T2) and 12 months post retention(T3) will be calculated for each variable.

RELAPSE DUE TO POOR COMPLIANCE:

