5.3 Ethics

A detailed protocol, ethical approval and site approval will be obtained from the KKM Ethics Committee before the study commenced. This research has been approved by the UKM Research Ethics Committee (Ethical approval number, UKM PPI/111/8/JEP-2018-724). All researchers in the study will adhere to the Good Clinical Practice Guidelines. A letter of consent will be obtained from each participant after explaining the nature and purpose of the study in verbal and in written. The data from the study will be made into a report which may be published. Participant's identity will be private and confidential, and will not be reported in any form of report. During the study, with respect to method of retention, if found in any patient for the relapse with VFR to be significant; new Hawley retainers (2-3 days) or retreat of fixed appliances (estimated 6-12 months) without any charge will be provided to the patient. Should subjects develop complications related to the study, treatment will be given at no cost at Faculty of Dentistry UKM Kuala Lumpur but subject will have to bear the travel expenses. Although theoretically the material of Hawley is more durable, there are no high quality long term studies comparing durability of both Hawley and VFRs. In fact long term follow-up studies have shown Hawley to have more breakages (Hitchens et al 2007). However if it does break, since it is an investigative product, we will replace the retainer with Hawley and subject will be considered dropout. During or after the study is completed, at any point if the research results are validated and if the modified VFR were found to be significantly less retentive than the Hawley retainer, subjects will be informed of the findings and new Hawley retainers will be provided to the modified VFR

group free of charge. If subject is not contacted regarding the results, it would mean that the modified vacuum is just as superior as the Hawley and the subjects in the modified vacuum can continue to use their retainer.

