5.4 Data management and analysis

Intra-examiner reliability of the measurements will be undertaken on two occasions in a random order and following an interval of two weeks.

A normality test will be conducted to determine whether a parametric or non-parametric test should be conducted. The outcome measures assessed will be the differences in means between groups, which will be assessed by one-way analysis of variance, using Statistical Package for Social Sciences (SPSS) version 17.0.

[4] -- Monday, July 08, 2019 -- 15:58:42

F tests - ANOVA: Repeated measures, between factors

Analysis: A priori: Compute required sample size

Input: Effect size f	=	0.42
α err prob	=	0.05
Power (1-β err prob)	=	0.80
Number of groups	=	2
Number of measurements	=	3
Corr among rep measures	=	0.5
Output: Noncentrality parameter λ	=	8.4672000
Critical F	=	4.1708768
Numerator df	=	1.0000000
Denominator df	=	30.0000000
Total sample size	=	32
Actual power	=	0.8038973

A reliability test will also be performed to calibrate the measurements made. The data will be reported in a collective manner with no reference to the specific individual. Publication policy by most journals would require removal of any personal details of any patient in any part of the article or in any supplementary materials (including all illustrations and videos) prior to submission, therefore the personal information from each individual will remain confidential. Access to the data is only by the research team (which involves orthodontists, dentists, personnel) and the REC UKM and KKM. The hard copy of the data obtained will be stored in a locked cupboard in a private room that could only be accessed by the research team. Soft copy of the data will be contained in a USB protection lock which password is only known to the research team. Data will be allowed for inspection or auditing by regulatory authorities. Data could be stored for at least 7 years before being destroyed (shredded) or deleted (electronic copy). Individuals have a right to know the results of their study and can contact the researchers if interested.

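### The no-contact rule in section 5.3 lets silence mean that the modified retainer is as good as the Hawley, which a non-significant difference test cannot show and a missed contact can make false

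*Combined protocol and SAP*

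**What the plan says.** Section 5.3 Ethics sets one trigger for contacting subjects about the group result. It applies once results are validated, and "if the modified VFR were found to be significantly less retentive than the Hawley retainer". In that case "subjects will be informed of the findings and new Hawley retainers will be provided to the modified VFR" arm at no cost. The text then gives a meaning to the absence of contact: "If subject is not contacted regarding the results, it would mean that the modified vacuum is just as superior as the Hawley". On that footing, those given the VFR may go on wearing it.

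Four other places bear on this:

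- Section 3.0 states a null hypothesis of no difference against an alternative of a difference. No equivalence or non-inferiority margin appears anywhere in the document.
- Section 5.1 sizes the trial at 16 per group for 80% power to detect 2.0 mm with SD 2.0 mm, and recruits 24 per group to allow for attrition.
- Section 1.0 gives the anticipated outcome: "We expect to see no difference between the modified vacuum formed retainer and Hawley retainer".
- Section 5.4 plans a one-way analysis of variance, prints a repeated-measures power output, and gives subjects one other route to the findings: "Individuals have a right to know the results of their study and can contact the researchers if interested".

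**The concern.** The rule ties a favourable conclusion to not being contacted, rather than to a result. Two quite different situations lead to silence, and the conclusion is unsafe in both.

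First, the result may be non-significant. A difference test that does not reject leaves open every value inside its confidence interval. Calling that equality is an inference the design was not built to make, and it would be drawn in exactly the outcome the team expects.

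Second, the result may be adverse but a VFR subject is not reached. The promise of a free Hawley retainer still stands, yet under the rule that subject's silence means the opposite of what was found. Section 5.4 allows subjects to ask for results, but the rule takes away the reason to ask.

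What is at stake is what participants are led to believe, and whether the promised replacement reaches them. The treatment estimate is unaffected.

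**Working it through.** **1. Reproduce the plan's figure.** Section 5.4 inputs: f = 0.42, N = 32, m = 3 measurements, correlation 0.5, alpha 0.05.

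lambda = f² × N × m / (1 + (m − 1) × 0.5) = 0.1764 × 32 × 3 / 2 = 8.467. The critical F(1, 30) is 4.171 and the power is 0.804. All three match the printed output.

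**2. See which difference that power refers to.** With two equal groups the difference is 2 × f × SD = 2 × 0.42 × 2.0 = 1.68 mm. A difference of 2.0 mm is f = 0.5. The 0.804 therefore belongs to 1.68 mm.

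**3. Chance of no significant adverse result.** This is the noncentral t probability below the critical value, two-sided alpha 0.05, with noncentrality = true deficit / SE and SE = SD × √(2/n).

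- One time point: SD = 2.0 mm (section 5.1). SE = 0.707 mm with n = 16 and 0.577 mm with n = 24.
- Repeated measures (section 5.4 model): SD of the mean of three = 2.0 × √((1 + 2 × 0.5)/3) = 1.63 mm. SE = 0.577 mm with n = 16 and 0.471 mm with n = 24.
- Critical t: 2.042 (30 df) and 2.013 (46 df). The 95% half-width is critical t × SE.

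| Model | n per group | True deficit 1.0 mm | True deficit 2.0 mm | 95% half-width |
|---|---|---|---|---|
| One time point | 16 | 72% | 22% | 1.44 mm |
| One time point | 24 | 60% | 8% | 1.16 mm |
| Repeated measures | 16 | 61% | 8% | 1.18 mm |
| Repeated measures | 24 | 45% | 1% | 0.95 mm |

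**4. Does a non-significant result exclude 2.0 mm?** If h is the half-width, a non-significant observed deficit is below h. The interval still contains 2.0 mm when the observed deficit is at least 2.0 − h.

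- One time point, 16 per group: yes, for observed deficits of 0.56 to 1.44 mm.
- One time point, 24 per group: yes, for 0.84 to 1.16 mm.
- Repeated measures, 16 per group: yes, for 0.82 to 1.18 mm.
- Repeated measures, 24 per group: never. The upper limit is below 2 × 0.95 = 1.90 mm, so 2.0 mm is always excluded.

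**5. Missed contact after an adverse result.** No arithmetic applies. The trigger clause says the subject should be told that the VFR is worse. The no-contact sentence says that a subject who has heard nothing may take it to be as good. For a subject who is not reached, both apply and they contradict each other. The available text describes no step to confirm that contact was made. At most 24 subjects could be affected, and only those still wearing the device.

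**The case against.** The strongest reply is that this is one loosely worded sentence in an ethics section, with real safeguards around it. Section 5.1 offers a free Hawley retainer for insignificant relapse and free treatment for significant relapse in the intervention group. Section 5.3 offers a new Hawley or retreatment without charge to any patient with significant VFR relapse, whatever the group result. Section 5.2 schedules checks for relapse at 3 and 6 months. This stands: the individual remedies protect a wearer whose relapse is noticed. They do not correct the meaning given to silence.

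It can also be said that significantly may carry a clinical sense here, since the same sections use the word for relapse in a single patient. That is possible. But with no margin stated, equality is unsupported under that reading too.

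Failed contact is hypothetical, and a protocol need not script every unanswered call. That is fair, and no frequency is claimed. The difficulty is that the plan attaches a reassuring meaning to non-contact.

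Three stronger readings are tempting, and the documents do not support them:

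- A reader might take the printed power of 0.804 as a 20% chance of missing 2.0 mm. It refers to 1.68 mm; under that model 2.0 mm is missed in about 8% of trials at 16 per group and 1% at 24.
- A reader might conclude that a non-significant result always leaves 2.0 mm open. That depends on the model and the number analysed, and fails for repeated measures with 24 per group.
- A reader might infer that participants are actually misled. The consent pages are not in the file, so whether they are told this rule is unknown.

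**Conclusion.** The no-contact sentence is wrong as written. It is unsupported after a non-significant result and false for a VFR subject who is not reached after an adverse one.

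The first part does not hinge on the choice of model: a true 1.0 mm deficit would produce no significant adverse result in 45% to 72% of trials across the four combinations examined. For a true 2.0 mm deficit the range is 1% to 22%, so the argument is much weaker at the plan's own clinically meaningful difference. These figures assume SD 2.0 mm, a two-sided 0.05 test as the trigger, 16 to 24 analysed per group and, for repeated measures, a correlation of 0.5 across three measurements.

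Severity is minor. Sample size, analysis and the trial estimate are untouched, and the individual remedies limit harm.

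**What to change.** Delete the no-contact sentence from section 5.3 and replace it with the following:

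- Send the overall result, in either direction, to every randomised subject. Section 5.2 already provides a route: "Researcher will send reminders of wearing retainer in 1-month interval".
- Describe a non-significant result as not having shown a difference, and give the estimated difference with its 95% confidence interval. Do not describe it as equality.
- If the result is adverse, follow up VFR subjects who have not responded, so that the promised free Hawley retainer reaches them.

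The cost is one edited paragraph, about 48 messages (2 × 24) and some follow-up calls in an arm of at most 24. If the consent material repeats the sentence, it needs the same change.

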5.4 Data management and analysis

Intra-examiner reliability of the measurements will be undertaken on two occasions in a random order and following an interval of two weeks.

A normality test will be conducted to determine whether a parametric or non-parametric test should be conducted. The outcome measures assessed will be the differences in means between groups, which will be assessed by one-way analysis of variance, using Statistical Package for Social Sciences (SPSS) version 17.0.

[4] -- Monday, July 08, 2019 -- 15:58:42

F tests - ANOVA: Repeated measures, between factors

Analysis: A priori: Compute required sample size

Input: Effect size f	=	0.42
α err prob	=	0.05
Power (1-β err prob)	=	0.80
Number of groups	=	2
Number of measurements	=	3
Corr among rep measures	=	0.5
Output: Noncentrality parameter λ	=	8.4672000
Critical F	=	4.1708768
Numerator df	=	1.0000000
Denominator df	=	30.0000000
Total sample size	=	32
Actual power	=	0.8038973

A reliability test will also be performed to calibrate the measurements made. The data will be reported in a collective manner with no reference to the specific individual. Publication policy by most journals would require removal of any personal details of any patient in any part of the article or in any supplementary materials (including all illustrations and videos) prior to submission, therefore the personal information from each individual will remain confidential. Access to the data is only by the research team (which involves orthodontists, dentists, personnel) and the REC UKM and KKM. The hard copy of the data obtained will be stored in a locked cupboard in a private room that could only be accessed by the research team. Soft copy of the data will be contained in a USB protection lock which password is only known to the research team. Data will be allowed for inspection or auditing by regulatory authorities. Data could be stored for at least 7 years before being destroyed (shredded) or deleted (electronic copy). Individuals have a right to know the results of their study and can contact the researchers if interested.

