3.0 HYPOTHESIS

There is a difference in the degree of relapse in terms of relapse of arch expansion between Modified Vacuum formed retainers and Hawley retainers.

NULL HYPOTHESIS

There is no difference in the degree of relapse in terms of arch expansion between Modified Vacuum formed retainers and Hawley retainers.

[figure not shown]

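### The planned one-way ANOVA names no width, visit or visit average, and the stated 80% power holds only if the visits are averaged; one named comparison adjusted for T0 width should be specified

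*Combined protocol and SAP*

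**What the plan says.** Section 5.4 gives the whole inferential plan in two sentences. The first makes the choice of test depend on the data: "A normality test will be conducted to determine whether a parametric or non-parametric test should be conducted". The second names the parametric option: "The outcome measures assessed will be the differences in means between groups, which will be assessed by one-way analysis of variance". No covariate, width, visit or multiplicity rule is given, and the non-parametric option has no name.

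The power output in the same section is headed "F tests - ANOVA: Repeated measures, between factors". It uses f = 0.42, alpha 0.05, two groups, three measurements and correlation 0.5, and returns a total of 32 with actual power 0.8038973. Section 5.1 describes the target differently: "to detect a clinically meaningful difference of 2.0mm (SD=2.0mm) between the two groups in terms of arch width differences". It then says: "To account for attrition, 24 patients will be recruited in each group".

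Sections 4.0 and 5.4.1 list canine, premolar and molar widths without ranking them. On the outcome itself, section 3.0 has "There is a difference in the degree of relapse in terms of relapse of arch expansion", which points to change, while the Executive Summary has "The arch width of subjects post-fixed appliances will be compared".

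The visits also differ by section. The clinical paragraph of section 5.2 and the monitoring table after it have follow-up impressions at 3 and 6 months. The data-analysis paragraph of section 5.2, section 5.4.1 and the Executive Summary add 12 months (T3).

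**The concern.** A reader cannot tell from section 5.4 what number the trial will report as its main result. Three widths, two or three follow-up visits and two candidate tests leave several possible primary results, and mixed results could be read either way. Section 5.3 adds weight, because it attaches consequences for participants to a finding that the modified retainer retains significantly less well, without saying which comparison would show this.

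The power claim is also exposed. It was computed for an average over three measurements. If the ANOVA is instead run at one visit, the 0.80 does not apply. In addition, T0 width is measured on every debond cast but is not used in the comparison, so available precision is given up.

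**Working it through.** **Inputs.** From the section 5.4 output: f = 0.42, N = 32, m = 3 measurements, correlation 0.5, alpha 0.05. From section 5.1: difference 2.0 mm, SD 2.0 mm, 16 per group, 24 per group recruited (48 in total). Assumed, because the documents do not give it: the correlation r between T0 width and follow-up width, taken as 0.5 to 0.9. Tests are taken as two-sided.

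**1. Reproduce the stated figure.** λ = f²·N·m / (1 + (m − 1)·0.5) = 0.42² × 32 × 3 / 2 = 8.467. With 1 and 30 df the critical F is 4.171 and power is 0.804. This matches the output.

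With two groups, this F test is the same as a one-way ANOVA on each patient's mean over the three measurements.

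**2. Average over two follow-up visits only.** If 3 and 6 months are the only follow-ups, m = 2 and λ = 0.42² × 32 × 2 / 1.5 = 7.526. Power is 75.6%.

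**3. One visit, unadjusted, f = 0.42.** λ = 0.42² × 32 = 5.645; power 63.3%. The smallest even N reaching 80% is 48 (81.3%), which is everyone recruited.

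**4. One visit, unadjusted, section 5.1 inputs.** The standardised difference is 2.0/2.0 = 1.0, so f = 1.0/2 = 0.50, not 0.42. λ = 0.50² × 32 = 8.0; power 78.1%, and 34 are needed (80.7%).

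The effect size f = 0.42 corresponds to 2 × 0.42 × 2.0 = 1.68 mm at an SD of 2.0 mm. At f = 0.50 the three-measurement test would need only 24 patients in total.

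**5. Effect of adjusting for T0 width, one visit.** Assume equal variance at T0 and follow-up, and that the 2.0 mm SD is the SD of change. The change score has variance 2σ²(1 − r) and the T0-adjusted outcome has σ²(1 − r²). The ratio is (1 + r)/2, so λ = f²·N / ((1 + r)/2), with N − 3 error df.

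| N = 32 | unadjusted change | adjusted, r = 0.5 | adjusted, r = 0.9 |
|---|---|---|---|
| f = 0.42 | 63.3% | 75.5% | 65.4% |
| f = 0.50 | 78.1% | 88.4% | 80.1% |

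If T0 explains nothing, the lost degree of freedom takes 63.3% to 63.2%.

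**6. Several widths.** Three independent tests at 0.05 give 1 − 0.95³ = 14.3% chance of at least one false positive. Simulation with 16 per group gives 12.5% at an assumed between-width correlation of 0.5, and 10.0% at 0.8.

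**The case against.** The strongest reply is that the planned test and the sizing test may be one and the same. Step 1 shows that a one-way ANOVA on patient means is exactly the test that was sized. This stands. A reader might infer that section 5.4 plans a different test from the one sized, but the documents show only that the tested quantity is unspecified.

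A second reply is that the trial is not clearly short of power. This stands in part. At section 5.1's figures a single-visit test has 78.1% at 32 patients and needs 34 of the 48 recruited, leaving 14 for attrition. The normal approximation for those figures, 2 × (1.960 + 0.842)² × (2.0/2.0)² = 15.7, also rounds up to 16 per group. The 63.3% requires both a single-visit reading and f = 0.42.

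A third reply is that adjusting for T0 is a preference and not a correction. It is true that leaving T0 out does not bias a randomised comparison, and that at high r the gain over change scores is small. It is still a better use of data already collected, at a cost of one degree of freedom.

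Two further readings are tempting but unsupported. One is that every width will be tested at every visit, with a correspondingly larger error rate; section 5.2 plans only descriptive statistics by visit. The other is that raw widths will be compared with a severe loss of power. That rests on a single Executive Summary sentence and on width SDs that the documents do not give, while section 3.0 and the relapse criteria in section 5.2 point to change.

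**Conclusion.** The concern holds as a failure to specify. No primary width, visit or average, fallback test or multiplicity rule is stated, and the 80.4% power is secured only if three measurements are averaged. The plan does not say so, nor does it say whether T0 is one of the three.

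If one visit is tested without adjustment, power at 32 patients is 63.3% or 78.1%, depending on which of the plan's two effect sizes is used. Testing each width once puts the chance of a false positive at about 10–14%, depending on the assumed correlation.

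A reader might infer that adjusting for T0 restores the power at no cost. It does not at f = 0.42 and N = 32 for a single visit: 75.5% at r = 0.5 and 65.4% at r = 0.9, if the 2.0 mm SD is that of change. The plan does not say which SD it means; if it is the SD of the width itself, the gain is larger (89.5% at r = 0.7).

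The randomised comparison remains valid. What is not secured is its stated power and its reading. This should be corrected before analysis.

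**What to change.** - Define relapse as change from T0. With T0 width as a covariate, change and follow-up width give the same arm difference, so the two descriptions of the outcome no longer conflict.
- Name one primary width. Intermolar is one candidate: section 5.2 speaks of the posterior region, and section 5.1 admits "Treatment plan of extraction or non-extraction followed by straight wire appliances in the upper arch only or both arches", so premolars may be missing in some patients.
- Make the primary comparison the average over the follow-up visits actually held, excluding T0 from the average. First reconcile the 12-month cast within section 5.2, and between the monitoring table on one side and the Executive Summary and section 5.4.1 on the other.
- Analyse by ANCOVA, or a mixed model over the follow-up visits, with arm and T0 width. Use this in place of the normality-test gate, with a residual check and a named rank-based sensitivity analysis. Report the adjusted difference with a 95% CI.
- Treat other widths and visits as secondary with Holm adjustment, or label them exploratory.
- Reconcile f = 0.42 with 2.0/2.0 mm, say which SD is meant, and restate power for the named comparison. If a single visit is preferred, size for that test.
- Reconcile the wording in section 5.3 about a significantly less retentive device with the analysis plan. The clinical trigger is for the investigators.

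**Cost.** Analysis-plan wording, a restated power calculation and one degree of freedom (about 0.1 point of power if T0 explains nothing). The adjustment needs no extra patients, casts or visits, since T0 is already measured and SPSS fits these models. The real price is that secondary widths no longer support stand-alone claims.
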